## Background

The main objective of this study is to compare the effectiveness of 10,600-nm carbon dioxide (C02) fractional laser and 1550-nm non-ablative laser (Fraxel) in the treatment of surgical and traumatic scars as well as identify the minimum number of treatments required to achieve the highest benefit at the lowest cost. This was a split-scar study, so each laser was randomly assigned to half of the scar and then each half of the scar was evaluated separately. Patients assessed scars prior to the first treatment (baseline) and 6 months after the last treatment using the Patient and Observer Scar Assessment Scale (POSAS). At both visits, photographs were taken using identical camera settings, lighting and patient positioning. Four blinded examiners then evaluated these photographs using the Manchester scar scale. There were 100 patients enrolled in the study and of those 83 have POSAS scores for the 6-month follow-up and 84 have photo evaluator scores for the 6-month follow-up (ID LSS108.2 was missing in the patient scores). The data was analyzed using SAS v9.4 software.

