## Hypotheses

- The ablative 10,600-nm carbon dioxide (C02) fractional laser and the 1550-nm non ablative laser (Fraxel) will both lead to improvement in the appearance of a surgical or traumatic scar as well as reduction of symptoms such as pain and itch.
- The ablative 10,600-nm carbon dioxide (C02) fractional will lead to a superior cosmetic outcome compared to the 1550-nm non-ablative laser (Fraxel) over the same number of treatments, thereby proving a more cost effective treatment.

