## **Analysis Approach**

First, we looked at the scoring distributions for each photo evaluator to check for differences in scoring patterns. Six paired t-tests were conducted to compare the total scores for all possible combinations of observers for each laser at both time points. Next, to assess the effectiveness of the C02 and Fraxel lasers, five paired t-tests were performed on both the patient self-scores and the photo evaluator scores from the 6-month follow-up:

- 1) C02 laser vs. Fraxel laser at baseline.
- 2) C02 laser vs. Fraxel laser at 6-month follow-up.
- 3) C02 laser at 6-month follow-up vs. C02 laser at baseline.
- 4) Fraxel laser at 6-month follow-up vs. Fraxel laser at baseline.
- 5) Difference in C02 laser after 6 months vs. difference in Fraxel laser after 6 months.

Paired t-tests compare whether the mean of the differences in two paired samples differs from 0. A statistically significant difference would indicate that the average scores are not the same for either the C02/Fraxel lasers or for each laser at different time periods.

We also used McNemar's test to investigate the agreement between the C02 and Fraxel lasers for both the POSAS and photo examiner scores, as well as the agreement between the POSAS and photo examiner scores for the C02 and Fraxel lasers separately.

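### Comparisons 2 to 5 use only the 83 or 84 of 100 enrolled patients with 6-month scores, with no check on whether the 16–17% loss could change the conclusions

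*SAP*

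**What the plan says.** The Background section of the SAP gives the counts: "There were 100 patients enrolled in the study and of those 83 have POSAS scores for the 6-month follow-up". For the photo scores the number is 84, and the SAP explains the gap of one by naming a single ID that lacks patient scores. There are two assessment times, baseline and 6 months after the last treatment. Patients rated their own scars on the POSAS before the first treatment. Photographs were taken at both visits and scored later by four blinded examiners.

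The Analysis Approach section says that "five paired t-tests were performed on both the patient self-scores and the photo evaluator scores from the 6-month follow-up". The first compares the two halves before treatment ("C02 laser vs. Fraxel laser at baseline"). The second compares them at 6 months. The third and fourth are before-after comparisons within one laser (for example "C02 laser at 6-month follow-up vs. C02 laser at baseline"). The fifth compares the two changes.

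Under Hypotheses, the first hypothesis is that the two lasers "will both lead to improvement in the appearance of a surgical or traumatic scar"; the second is that the ablative laser gives the better cosmetic result. Neither is restricted to patients who came back. The SAP names no method for missing 6-month scores, no comparison of patients with and without follow-up, and no sensitivity analysis.

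**The concern.** A paired t-test uses only complete pairs. Comparisons 2 to 5 each need a 6-month score, so about one patient in six contributes nothing to them. The completer mean represents the enrolled group only if the loss is unrelated to what is being estimated.

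The split-scar design helps less than it may seem, and unequally across the comparisons:

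- **Comparisons 3 and 4** set a scar half against itself over time. Nothing cancels. If patients who improved less, or whose baseline severity predicts a different change, were less likely to return, the mean change is biased directly. The first hypothesis rests on these two tests.
- **Comparisons 2 and 5** lose both halves of a scar together. An effect of loss shared by the halves cancels in the within-patient difference. Bias remains only if return depends on the difference between the halves, for instance if one half healing worse than the other led a patient to stop attending.

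At stake are the size and confidence interval of the reported improvement, and the significance of a modest difference between the lasers.

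**Working it through.** **Counts.** 84 with photo scores, less the one ID named as lacking patient scores, gives 83 with POSAS scores, as stated. Missing: 100 − 83 = 17 (17%) for POSAS and 100 − 84 = 16 (16%) for photos. The SAP gives no SD, effect size or alpha. Everything below is therefore in SD units of the paired difference concerned, with a two-sided 5% level assumed.

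**Shift in the completer mean.** Shift = missing share × gap between the means of returners and non-returners. For POSAS the SE is 1/√83 = 0.110 SD. With b = shift/SE, the coverage of a nominal 95% interval is Φ(1.96 − b) − Φ(−1.96 − b).

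| Assumed gap (SD) | Shift at n = 83 (SD) | b | Coverage |
|---|---|---|---|
| 0.25 | 0.17 × 0.25 = 0.0425 | 0.39 | about 93% |
| 0.5 | 0.17 × 0.5 = 0.085 | 0.77 | about 88% |
| 1.0 | 0.17 × 1.0 = 0.17 | 1.55 | about 66% |

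For the photo scores (n = 84, SE 0.109 SD) the shifts are 0.04, 0.08 and 0.16 SD.

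**Why the contrast differs from the before-after tests.** Take a normal selection model at n = 83 with an assumed correlation of 0.6 between the two halves' changes. If loss correlates 0.3 with the change in each half, the before-after bias is 0.091 SD for each laser, but the contrast bias is zero and its error rate stays at 5%. If the correlations are 0.3 and 0.1, or 0.3 and 0, the contrast bias is 0.061 or 0.091 SD (of a single half's change), and a nominal 5% test rejects a true null about 9.5% or 15% of the time.

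**Tipping point for the laser contrast.** Let d be the completer mean difference and x the mean difference in the 17 missing patients. The whole-cohort mean is 0.83d + 0.17x. With the SD held at 1 and n = 100, significance needs 1.984 × 0.10 = 0.198. Solving for x:

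- d = 0.25: (0.198 − 0.2075)/0.17 ≈ −0.05 SD
- d = 0.30: (0.198 − 0.249)/0.17 ≈ −0.30 SD
- d = 0.50: (0.198 − 0.415)/0.17 ≈ −1.27 SD

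The last figure is approximate: so large a gap would itself widen the spread, and significance would be lost somewhat sooner.

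**No change in the missing patients (comparisons 3 and 4).** The completer mean would overstate the whole-cohort change by 1/0.83 = 1.20, that is by 20%. The test hardly moves. For a completer change of 0.5 SD, t = 0.5 × √83 = 4.56. With zeros filled in, the mean is 0.415, the variance is 0.83 + 0.83 × 0.17 × 0.25 = 0.865, and t = 0.415/(√0.865/10) = 4.46.

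**The case against.** Much of the case on the other side stands.

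- **A reader might infer that dropout was related to outcome and that the results are therefore biased.** The SAP does not support this. It gives no reasons for loss, and the patient who leaves because one half healed badly is hypothetical. The claim must be conditional.
- **A reader might infer that all five comparisons are affected.** Comparison 1 needs baseline scores only. The phrase tying all five tests to 6-month scores cannot be literal, since comparisons 1, 3 and 4 use baseline values. The point is confined to comparisons 2 to 5.
- **A reader might assume that baseline scores exist for all 100 patients on both scales.** Only the POSAS ratings are placed before the first treatment, and even for these the SAP does not say that all 100 were obtained. Photographs were scored later, and nothing says that the non-returners' baseline pictures were scored.
- **Strong effects survive.** A contrast of 0.5 SD is hard to overturn, and contrasts of 0.25 and 0.30 SD stay significant if the missing patients show no laser difference at all (0.2075 and 0.249 against 0.198). The first hypothesis asserts improvement, not a size, and its test survives the no-change scenario.
- **A mixed model cannot do everything.** With two visits it corrects only for loss explained by observed baseline scores. Because the lasers were randomised to halves, it will largely reproduce the completer contrast. The SAP is also written in the past tense, so silently swapping the main analysis would be a post hoc change.
- **The SAP reports both denominators openly and does not claim that the results cover all 100.**

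What these points do not remove is that the SAP reports a loss of 16–17% and fixes an analysis that ignores it. Not knowing why patients are missing is the reason to examine how sensitive the answer is.

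**Conclusion.** The point holds in conditional form and should be acted on. Comparisons 2 to 5 rest on 83% (POSAS) or 84% (photo) of enrolled patients. If loss relates to baseline severity or outcome, the before-after estimates are biased. The laser contrasts are biased only if loss relates to the difference between the halves.

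Under the assumed gaps of 0.25 to 1 SD, the effect on a POSAS mean ranges from minor (coverage about 93%) to serious (about 66%). For the first hypothesis the risk lies mainly in the size and precision of the improvement. For the second it lies in a modest contrast: one of 0.25–0.30 SD could lose significance with a missing-patient mean of about −0.05 to −0.30 SD, whereas one of 0.5 SD would need about −1.27 SD. All SD-unit figures are assumptions; the SAP supplies only the counts. Neither the existence nor the direction of any bias can be established from it.

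**What to change.** 1. For each scale, fit a linear mixed model to all available scores: one score per half and visit (the average of the four examiners for photos), fixed effects for laser, visit and laser-by-visit, and an unstructured covariance within patient. Take the contrasts that correspond to comparisons 2 to 5. Non-returners then contribute their baseline scores where these exist (POSAS, and photos if the baseline pictures were scored).
2. Keep the paired t-tests and label them as the completer analysis, so that the added model is visible as an addition.
3. Report the reasons for missing follow-up where known, and compare baseline scores by follow-up status.
4. Add a delta-adjusted (tipping-point) analysis that shifts the missing change (comparisons 3 and 4) and the missing laser difference (comparisons 2 and 5), including the scenarios of no change and of a reversed laser difference. This carries most of the weight, since the model cannot address loss driven by unobserved outcomes.
5. If a plausible shift overturns a conclusion, limit that conclusion to patients who returned.

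The cost is some SAP wording and a short additional SAS program, with no new patient visits. The estimates may turn out less favourable or less precise.

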## Hypotheses

- The ablative 10,600-nm carbon dioxide (C02) fractional laser and the 1550-nm non ablative laser (Fraxel) will both lead to improvement in the appearance of a surgical or traumatic scar as well as reduction of symptoms such as pain and itch.
- The ablative 10,600-nm carbon dioxide (C02) fractional will lead to a superior cosmetic outcome compared to the 1550-nm non-ablative laser (Fraxel) over the same number of treatments, thereby proving a more cost effective treatment.

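### Hypothesis 2 treats cosmetic superiority at equal treatment numbers as proof of cost-effectiveness; this does not follow, and every analysis the SAP lists uses scar scores only

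*SAP*

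**What the plan says.** SAP, Hypotheses: the second hypothesis is that the CO2 laser will be cosmetically superior to Fraxel "over the same number of treatments, thereby proving a more cost effective treatment". The final clause is worded as a consequence of the first, not as a separate hypothesis with its own test.

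SAP, Background: the main objective also includes an aim to "identify the minimum number of treatments required to achieve the highest benefit at the lowest cost". On design, "each laser was randomly assigned to half of the scar and then each half of the scar was evaluated separately". On timing, "Patients assessed scars prior to the first treatment (baseline) and 6 months after the last treatment"; photographs for the blinded examiners were taken at the same two visits.

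SAP, Analysis Approach: five paired t-tests are run on the patient scores and on the photo evaluator scores. Two of them compare the lasers after treatment: Test 2, "C02 laser vs. Fraxel laser at 6-month follow-up", and Test 5, "Difference in C02 laser after 6 months vs. difference in Fraxel laser after 6 months". The section also lists paired t-tests between observers and McNemar's tests of agreement. It reads significance as follows: "A statistically significant difference would indicate that the average scores are not the same for either the C02/Fraxel lasers", or for one laser at two times.

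**The concern.** A cost-effectiveness statement needs costs as well as effects. Hypothesis 2 supplies an effect comparison and an equal session count, and draws a cost-effectiveness conclusion from these two alone. Equal session counts remove one source of cost difference but leave the cost per session open.

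Tests 2 and 5 are the natural tests of the cosmetic part of Hypothesis 2. If either is significant in favour of CO2, the hypothesis as worded lets the report go on to say that CO2 has been shown to be more cost effective. Nothing in the listed analyses would support that sentence.

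A smaller matter of the same kind concerns the Background aim on treatment number. A favourable result at follow-up could be taken as answering it, although no listed test uses treatment number.

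**Working it through.** The SAP states no figure on this point, so there is none to reproduce. The check is one of logic, with an illustration.

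**Does superiority at equal sessions imply cost-effectiveness?**

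Let each half receive k sessions (Hypothesis 2's premise; k is not given in the SAP). Let c_C and c_F be the cost per session and E_C and E_F the improvement, taken as positive, for CO2 and Fraxel.

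- Total costs are k × c_C and k × c_F. Their difference is k × (c_C − c_F), which equal k does not make zero.
- Cost per unit of improvement, CO2 relative to Fraxel, is (k × c_C / E_C) ÷ (k × c_F / E_F) = (c_C / c_F) ÷ (E_C / E_F). The k cancels. CO2 is favoured when c_C / c_F < E_C / E_F.
- If E_C > E_F and c_C ≤ c_F, the condition always holds, so superiority alone is enough.
- If E_C > E_F and c_C > c_F, the condition may hold or fail, depending on the two ratios.

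The SAP gives neither session cost, makes no equal-cost assumption and places no value on an improvement in score. It therefore does not show which case applies.

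**Illustration.** All ratios here are assumptions; none comes from the SAP. Take E_C / E_F = 1.2, that is, 20% more improvement with CO2.

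| Assumed c_C / c_F | Cost per unit of improvement, CO2 ÷ Fraxel | Favours |
|---|---|---|
| 0.8 | 0.8 / 1.2 = 0.67 | CO2 |
| 1.0 | 1.0 / 1.2 = 0.83 | CO2 |
| 1.1 | 1.1 / 1.2 = 0.92 | CO2 |
| 1.2 | 1.2 / 1.2 = 1.00 | neither |
| 1.5 | 1.5 / 1.2 = 1.25 | Fraxel |
| 2.0 | 2.0 / 1.2 = 1.67 | Fraxel |

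The same cosmetic superiority fits CO2 being more, equally or less cost effective.

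**Does any listed analysis use cost or treatment number?**

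| Analysis | Compares | Cost | Treatment number |
|---|---|---|---|
| Observer t-tests | Total scores between pairs of observers | no | no |
| Test 1 | Scores of the two halves before treatment | no | no |
| Test 2 | Scores of the two halves at follow-up | no | no |
| Tests 3 and 4 | Follow-up with baseline within each laser | no | no |
| Test 5 | Change in score between lasers | no | no |
| McNemar's tests | Agreement between lasers and between score sources | no | no |

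The effectiveness t-tests number 5 × 2 score sources = 10; 0 use cost and 0 use treatment number.

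**Treatment number.** Tests 2 and 5 compare two halves that, on Hypothesis 2's premise, differ by k − k = 0 sessions. Tests 3 and 4 compare the untreated scar with its state after the whole course. The SAP describes scores at those two times only, and no listed test is stratified by or adjusted for session count.

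**The case against.** The strongest reply is that the Analysis Approach already keeps interpretation in bounds. It presents the t-tests as assessing effectiveness and reads a significant result only as a difference in average scores. The overreach sits in a hypothesis statement, and no decision rule carries it forward. This softens the harm and is fair as far as it goes. It does not withdraw the inference, however: the Hypotheses section still says that superiority proves cost-effectiveness, and the two sections point a reader in different directions.

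A second reply is that the protocol, not at hand, may hold a cost analysis. It may, and the absence of one here is not the complaint. A cost analysis elsewhere could support a cost-effectiveness conclusion on its own evidence, but it would not make the step from scores alone valid.

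A third reply is that the treatment-number point is mainly an omission that the protocol may cover. That stands, which is why the point is secondary and confined to the analyses listed in the SAP.

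Three stronger readings are tempting and not supported:

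- A reader might infer that CO2 can be more cost effective only if its sessions cost no more. That is the condition for superiority alone to be enough. With the assumed 20% extra benefit, a session costing 10% more still gives 0.92, in favour of CO2.
- A reader might infer that no scores were taken between sessions. The SAP describes two assessments; it does not say there were no others.
- A reader might infer that any comparison by session count would be observational. The SAP says that laser was randomised to scar halves, but not how the number of sessions was set.

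**Conclusion.** The point holds for the cost clause. As written, Hypothesis 2 draws a cost-effectiveness conclusion that the score comparisons cannot carry. That superiority alone does not suffice is a matter of logic and rests on no assumed figure; the illustration only shows that the answer can go either way.

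The size of any cost error cannot be computed, because the SAP gives no session costs, session counts or value per unit of score. No estimate or p-value is affected. The effect is on what may be concluded: a significant Test 2 or 5 in favour of CO2 supports a statement about scar scores and no more. This is worth correcting, because the clause is part of a stated hypothesis and the remedy is almost free.

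The secondary point holds in limited form: the listed analyses do not address the aim on treatment number. It does not follow that the trial as a whole cannot address it.

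**What to change.** Either of two changes to Hypothesis 2 would do:

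1. Limit it to cosmetic superiority by removing the closing clause on cost-effectiveness.
2. If it is kept as written for transparency, which is reasonable since the SAP describes its analyses in the past tense, add: *Tests 2 and 5 compare scar scores only; a significant result does not establish cost-effectiveness, which the analyses listed here do not test.*

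In addition, state in the Analysis Approach: *The analyses listed here do not address the smallest number of treatments needed, since none uses treatment number and scores are described only at baseline and at the follow-up after the final session.* If another document holds an analysis of cost or treatment number, cite it at this place.

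The cost is one or two sentences, with no new data and no re-analysis. The downside is a narrower claim.

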## **Analysis Approach**

First, we looked at the scoring distributions for each photo evaluator to check for differences in scoring patterns. Six paired t-tests were conducted to compare the total scores for all possible combinations of observers for each laser at both time points. Next, to assess the effectiveness of the C02 and Fraxel lasers, five paired t-tests were performed on both the patient self-scores and the photo evaluator scores from the 6-month follow-up:

- 1) C02 laser vs. Fraxel laser at baseline.
- 2) C02 laser vs. Fraxel laser at 6-month follow-up.
- 3) C02 laser at 6-month follow-up vs. C02 laser at baseline.
- 4) Fraxel laser at 6-month follow-up vs. Fraxel laser at baseline.
- 5) Difference in C02 laser after 6 months vs. difference in Fraxel laser after 6 months.

Paired t-tests compare whether the mean of the differences in two paired samples differs from 0. A statistically significant difference would indicate that the average scores are not the same for either the C02/Fraxel lasers or for each laser at different time periods.

We also used McNemar's test to investigate the agreement between the C02 and Fraxel lasers for both the POSAS and photo examiner scores, as well as the agreement between the POSAS and photo examiner scores for the C02 and Fraxel lasers separately.

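### The 6-month and change-score t-tests both address the one laser-superiority hypothesis and are not ranked; a baseline-adjusted paired regression, labelled post hoc, would be a better main estimate

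*SAP*

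**What the plan says.** The SAP's Hypotheses section has a single between-laser claim: the CO2 laser "will lead to a superior cosmetic outcome compared to the 1550-nm non-ablative laser (Fraxel").

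Under Analysis Approach, "five paired t-tests were performed on both the patient self-scores and the photo evaluator scores from the 6-month follow-up". Two items in that list bear on the between-laser claim:

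- Test 2: "C02 laser vs. Fraxel laser at 6-month follow-up".
- Test 5: "Difference in C02 laser after 6 months vs. difference in Fraxel laser after 6 months".

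Test 1 is a baseline check. Tests 3 and 4 are within-laser changes and serve the other hypothesis, that both lasers improve the scar. No test is named as the deciding one. The only guidance on reading a result is general: "A statistically significant difference would indicate that the average scores are not the same for either the C02/Fraxel lasers", or that one laser's scores differ between times.

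The Background section gives the design, "each laser was randomly assigned to half of the scar and then each half of the scar was evaluated separately", and the timing of the patient scores, "Patients assessed scars prior to the first treatment (baseline) and 6 months after the last treatment". Photographs for the examiners were taken at the same two visits, so both outcomes have a baseline score for each half. The analysis is described as already done: "The data was analyzed using SAS v9.4 software".

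**The concern.** Randomisation within the scar makes the expected baseline difference between halves zero. Tests 2 and 5 therefore estimate the same laser effect. They differ only in how much of the observed baseline difference they subtract: none in Test 2, all of it in Test 5. Either would be a valid sole test. With both listed and neither ranked, there are two problems.

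- If one is significant and the other is not, the reader cannot tell which answers the superiority hypothesis. If either may carry the claim, the false-positive chance per outcome exceeds the nominal level.
- The collected baseline enters with a fixed weight of 0 or 1, when the data could supply the weight. Precision is lost unless the best weight happens to be close to the one chosen.

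**Working it through.** The SAP gives no alpha, SD, correlation or power, so there is no figure of its own to reproduce.

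**Inputs.** From the SAP (Background): 83 patients with 6-month POSAS scores and 84 with photo scores; 83 is used here. Assumed: two-sided 0.05, normally distributed differences, and ranges for the two quantities below.

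**Notation.** For each patient, D0 is the CO2-minus-Fraxel difference at baseline and D1 the same difference at 6 months. Let r = corr(D0, D1), taken as 0, 0.1, 0.3, 0.5 and 0.7, and k = SD(D0)/SD(D1), taken as 0.1, 0.3, 0.5, 0.7 and 1.

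**Large-sample variances, in units of Var(D1)/n.**

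- Test 2 (mean of D1): 1
- Test 5 (mean of D1 − D0): 1 + k² − 2rk
- Intercept from regressing D1 on D0: 1 − r²

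Test 2 minus adjusted = r². Test 5 minus adjusted = 1 + k² − 2rk − 1 + r² = (k − r)². Neither can be negative. The adjusted variance ties with Test 2 only at r = 0 and with Test 5 only at r = k. Over the grid it is 51% (r = 0.7) to 100% of Test 2's, and 50% (k = 1, r = 0) to 100% of Test 5's.

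**Type I error if either test may carry the claim.** The correlation of the two test statistics is (1 − rk)/√(1 + k² − 2rk). For k = 1, r = 0.5 this is 0.5/√1 = 0.5, and the bivariate normal gives 9.1%. Across r:

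| k | Either-test type I error |
|---|---|
| 0.1 | 5.4–5.5% |
| 0.3 | 6.2–6.4% |
| 0.5 | 7.1–7.3% |
| 0.7 | 7.7–8.3% |
| 1 | 8.3–9.4% |

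Under no effect, the chance of opposite verdicts is twice the either-test error minus 10 points, which is about 0.7% to 9% over the grid.

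**Power.** Set the effect so that the adjusted analysis has 80% power. In large samples Test 2 then has power Φ(2.80·√(1 − r²) − 1.96). At r = 0.7 this is Φ(2.80 × 0.714 − 1.96) = Φ(0.04), or 52%. For Test 5, replace √(1 − r²) by √[(1 − r²)/(1 + k² − 2rk)]. At k = 1, r = 0.7 this is √(0.51/0.60) = 0.922, and Φ(2.80 × 0.922 − 1.96) = Φ(0.62), or 73%.

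Monte Carlo at n = 83 (100,000 trials per cell) agrees:

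| k | r | Slope r/k | Test 2 power | Test 5 power | Adjusted power | Tests 2 and 5 disagree |
|---|---|---|---|---|---|---|
| 0.1 | 0 | 0 | 80.3% | 79.9% | 79.8% | 2.4% |
| 0.1 | 0.7 | 7 | 52.0% | 57.7% | 80.0% | 5.8% |
| 0.3 | 0.3 | 1 | 76.8% | 80.3% | 79.9% | 7.6% |
| 0.5 | 0.5 | 1 | 68.4% | 80.5% | 80.0% | 16.7% |
| 1 | 0 | 0 | 80.6% | 51.4% | 80.0% | 33.3% |
| 1 | 0.3 | 0.3 | 76.5% | 62.0% | 79.8% | 28.4% |
| 1 | 0.7 | 0.7 | 52.4% | 73.9% | 80.2% | 39.0% |

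Across all 25 cells the intercept test had type I error of 4.9–5.1%. At this effect, disagreement was 2–6% (k = 0.1), 7–18% (0.3), 12–27% (0.5), 18–33% (0.7) and 28–39% (1).

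**The case against.** The strongest reply has five parts.

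- **The protocol may name the deciding comparison.** This is possible, and the fix gives way to it. But saying which of its own listed tests answers its own hypothesis is a SAP's task.
- **The SAP never says that either test may carry the claim.** This is correct. Its sentence on significance explains what a paired t-test shows and is not a decision rule. The inflated error therefore applies only if the open choice is used that way.
- **Each test is valid, so adjustment is only a matter of efficiency.** This is true of each test alone. It does not remove the ambiguity between them.
- **The grid includes unlikely cells.** Six of the 25 have a slope r/k above 1 (1.4 to 7), meaning a baseline difference between halves would grow by 6 months. If the slope is at most 1, Test 2 keeps relative efficiency of at least 1 − k²: 99% at k = 0.1, 91% at k = 0.3 and 75% at k = 0.5. The 52% power at k = 0.1, r = 0.7 should therefore carry little weight. Large losses also occur at slopes of 1 or less, as at k = 0.7, r = 0.7 and k = 1, r = 0.7, but they need the untreated halves to differ from each other nearly as variably as the treated halves do.
- **A third analysis chosen after the data adds another path.** It does, so all three results must be shown and no error control claimed.

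Two limits remain. The two instruments are themselves unranked, which this point does not settle. The SAP also does not say how four examiners' scores become one score per patient.

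**Conclusion.** The concern holds and should be fixed, though it does not invalidate the trial. That the tests are unranked, and that the adjusted estimate is never less precise than either in large samples, does not depend on the assumed values. The size does: it rests on r and k, which the SAP does not give, and on a two-sided 0.05 level with normal differences. If the halves scored almost alike at baseline (k near 0.1), the error is about 5.5% and the tests rarely disagree. If baseline and 6-month differences vary equally (k = 1), the error reaches 9.4%, and at a real effect the two tests can disagree in up to 39% of trials. Confidence in the practical importance is moderate.

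**What to change.** For each outcome, regress each patient's 6-month CO2-minus-Fraxel difference on the baseline CO2-minus-Fraxel difference, using the same per-patient scores as Tests 2 and 5. Enter the baseline difference uncentred, so that the intercept is the laser effect at zero baseline difference; centring it on the sample mean would return Test 2's estimate. Report the intercept with its 95% confidence interval as the main between-laser estimate. If the protocol already names the deciding comparison, keep that choice and show the adjusted estimate as supportive.

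Show Tests 2 and 5 beside it whatever they find. State that this ranking was made post hoc, after the data had been analysed, and that it does not restore error control.

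The cost is one regression per outcome on data already held, a sentence of SAP wording, and a third between-laser result to report. Where the adjusted analysis has nothing to gain (r = 0 against Test 2, r = k against Test 5), it loses about 0.5 percentage points of power at n = 83.

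### McNemar's test is used to measure agreement between the two lasers, which it cannot do, and the SAP states no yes/no outcome for it

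*SAP*

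**What the plan says.** After the paired t-tests, the SAP's Analysis Approach adds: "We also used McNemar's test to investigate the agreement between the C02 and Fraxel lasers for both the POSAS and photo examiner scores". The sentence goes on to a second use, "as well as the agreement between the POSAS and photo examiner scores for the C02 and Fraxel lasers separately". This point concerns the first use, the comparison of one laser with the other.

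Everywhere else the section handles these outcomes as numbers. For the photo raters, "Six paired t-tests were conducted to compare the total scores for all possible combinations of observers for each laser at both time points". For efficacy, "five paired t-tests were performed on both the patient self-scores and the photo evaluator scores from the 6-month follow-up". The Background names the instruments: patients used POSAS, and "Four blinded examiners then evaluated these photographs using the Manchester scar scale". On the amount of data it reports that, of 100 patients enrolled, "83 have POSAS scores for the 6-month follow-up and 84 have photo evaluator scores for the 6-month follow-up".

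For the McNemar analysis the SAP does not state:
- a responder definition or cut-point on either scale;
- whether the 6-month score or the change from baseline is used;
- how four examiners' scores become one yes/no per scar half;
- whether the exact or the chi-square version is used;
- how the result is to be read.

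**The concern.** There are two faults. First, the test is given a job that it does not do. McNemar's test asks whether the proportion of successes is the same under the two lasers. Agreement asks how often the two halves of a scar fall in the same category. These are different quantities, and the Hypotheses section asks neither for agreement nor for equivalence: it predicts a better cosmetic result with the CO2 laser.

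Second, the test has no stated input. It cannot be computed from a multi-point score until someone turns that score into yes or no. Two analysts following this text could choose different rules and report different results. Deriving a binary outcome for a named test is ordinary SAP content, so this is not a matter that can simply be left to the protocol.

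At stake is a second answer to the laser comparison on both outcomes. It is weaker than Tests 2 and 5 and depends on the cut. Its label also invites a non-significant result to be taken as similarity.

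**Working it through.** The SAP gives no power figure, alpha, cut-point or McNemar result, so there is nothing of its own to reproduce. The only input taken from it is n = 83 pairs (POSAS at follow-up, Background). Two-sided 0.05 is assumed throughout.

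**1. Does the p-value track agreement?** Write a paired table as a/b/c/d: a = both halves yes, b = CO2 only, c = Fraxel only, d = neither. Agreement is (a + d)/n. McNemar's exact test uses only b and c: under the null hypothesis, b is binomial with b + c trials and probability 0.5. The cells that carry the agreement, a and d, do not enter the test.

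| Table (n = 83) | Agreement | Kappa | Exact p |
|---|---|---|---|
| 0/41/42/0 | 0/83 = 0% | -1.0 | 1.00 |
| 20/21/21/21 | 41/83 = 49% | -0.01 | 1.00 |
| 40/7/0/36 | 76/83 = 92% | 0.83 | 2 × 0.5^7 = 0.016 |

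Total disagreement and chance-level agreement both give p = 1.00, and high agreement gives a significant result. These are constructed tables. They show that the p-value can run opposite to agreement, whatever cut is used.

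**2. Power lost by dichotomising.** Assumptions: bivariate normal scores, within-scar correlation r of 0.5, 0.7 or 0.85, and a true shift of 0.32 SD of the paired difference. In SDs of a single score the shift is 0.32 × √(2(1 − r)), that is 0.32, 0.25 and 0.18.
- Paired t-test: the non-centrality is 0.32 × √83 = 2.92, and the power is about 0.82 at every correlation.
- Exact McNemar at the median cut, by simulation: 0.43, 0.34 and 0.25. Independent repeats stayed within 0.02 of these.
- Non-significant in 1 − power = 57%, 66% and 75% of such trials, although the difference is real.

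Part of this loss comes from the conservatism of the exact test, which rejects in about 3% of null trials at one median cut. The uncorrected chi-square does somewhat better but still falls short. At correlation 0.5 and a shift of 0.3 SD it rejected in 46% of simulated trials. The t-test there has non-centrality 0.3 × √83 = 2.73 and power of about 0.77.

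**3. Dependence on the cut.** In one simulated data set (correlation 0.7, shift 0.3 SD of a single score), cuts at −1, −0.5, 0, 0.5 and 1 SD gave exact p = 0.039, 0.0014, 0.076, 0.021 and 0.39. If there were no true difference and someone kept the best of these five cuts, the false-positive rate would be about 11% to 13% with the exact test (0.131, 0.120 and 0.115 at the three correlations). With the uncorrected chi-square it would be about 20%.

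**The case against.** The strongest reply is that the evidence for misuse is thin.

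- *Timing of the cut.* A reader might infer from the past tense and the known follow-up counts that a cut was picked after looking at the data. The document does not show this. It shows that the text was written after follow-up and records no pre-set rule. It does not show when or how a rule was set, and the protocol, which is not at hand, may contain one.
- *Several cuts.* Nothing in the SAP suggests that more than one was tried. The 11% to 13% and 20% figures describe what selection would do, not what was done. At a single median cut the exact test is conservative.
- *Reading of non-significance.* A reader might infer that a non-significant result was to be reported as the lasers agreeing. No such rule is given. The section's one interpretive statement, "A statistically significant difference would indicate that the average scores are not the same for either the C02/Fraxel lasers", with the continuation on time periods, concerns the t-tests and never equates non-significance with equality. The 57% to 75% are rates of non-significance under assumed inputs, not predictions of what the investigators would write.
- *Importance.* The analysis comes after five t-tests that address the hypotheses directly.

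All of this stands, and it limits the size of the point. It does not touch the two facts on the page: the test is said to investigate agreement, which it does not measure, and no binary outcome is stated for it.

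**Conclusion.** The stated analysis is wrong as written, whatever cut was used. McNemar's test compares marginal proportions, so neither a significant nor a non-significant result says how far the lasers agree, and a non-significant one is not evidence that they perform alike. The absence of a stated dichotomisation also means that the result cannot be reproduced from the SAP.

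The first conclusion rests on the definition of the test and on the constructed tables, with no distributional assumption. The loss of power, from about 82% to between 43% and 25%, rests on normal scores, correlations of 0.5 to 0.85, a median cut and the exact test, none of which the SAP gives. The inflation figures hold only if several cuts were tried. The SAP does not support a charge of post hoc cut selection, or of non-significance having been read as equivalence. Because Tests 2 and 5 carry the laser comparison, this is a modest correction that should be made, not one that undermines the trial's main analysis.

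**What to change.** Remove McNemar's test as an agreement analysis between the lasers. Base the laser comparison on the paired mean difference in Tests 2 and 5, each reported with its 95% CI.

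If a responder summary is kept:
- state the yes/no rule actually used on each scale, its time point, and how the four examiners' scores are combined;
- call it a paired comparison of responder proportions, and report the difference with a 95% CI;
- name the version of the test;
- label it exploratory unless the rule can be shown to have been pre-set;
- say that non-significance is not evidence of equality.

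Replacing the missing rule with one such as any improvement from that half's own baseline would not solve the problem. It is itself a cut, at zero change, and the Hypotheses section expects both lasers to improve scars, so most halves could count as responders. For the same 0.32 SD shift, exact McNemar power under that rule would be about 0.22, 0.17 and 0.11 (correlations 0.5, 0.7 and 0.85) if the mean improvement were 1 SD of the change score. It would be about 0.09, 0.05 and 0.02 at 1.5 SD. Both improvements are assumed.

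The cost is SAP wording and at most one re-run on existing scores. One supplementary p-value per outcome is dropped or demoted.
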